- Health and Mobility Questionnaires. Several questionnaires will be used to determine health, mobility, psychosocial status, and medication usage; these measures will be used to control for non-neural factors that may contribute to cognitive health. Questionnaires to be administered include: Beck Depression Inventory (depression screen), medication usage form (list of current medications), health survey questionnaire (inventory of health status and activity level), and life space questionnaire (mobility inventory).

Attention Battery

The goal of Specific Aim 1 is to construct a cognitive battery that decomposes the general construct of attention into its underlying mechanisms, enabling the examination of chemotherapy-related impairments across multiple processes of attention. To this end, we selected tasks that isolate four mechanisms of attention: 1) *processing speed* – time required to attend and recognize an item, 2) *inhibitory control* – ability to ignore irrelevant items, 3) *disengagement speed* – time required to release attention from an item, and 4) *storage capacity* – number of items that can be simultaneously attended.

Attention mechanisms measured by our battery are relevant to daily activities in the real world, such as holding a conversation in a noisy diner. For example, while listening to a friend speaking (i.e. target stimulus), the sounds of other patrons speaking (i.e. irrelevant stimulus) or dishes crashing to the floor (i.e.

distractor stimulus) compete for our limited attentional resources, thus providing opportunities for our attention to be distracted away from our friend speaking and towards an irrelevant stimulus. This hypothetical scenario provides examples of the four attention mechanisms measured in Specific Aim 1: speed at which speech of friend can be processed to understanding (*processing speed*), ability to ignore other patrons speaking and dishes crashing (*inhibitory control*), speed at which attention can be released from a distracting stimulus and re-engaged with the conversation (*disengagement speed*), and how much information from the conversation can be held in memory (*storage capacity*).

Collectively, our cognitive battery will offer millisecond-by-millisecond resolution of attention processes engaged by participants during task performance.

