In this task (Figure 3), participants are instructed to remember the value (e.g. orientation) of target items (e.g. blue lines) during a blank delay period (storage condition); on some trials, participants are instructed to ignore distractor items (e.g. red lines) presented simultaneously among target items (filtering condition). Performance is measured as response accuracy of correctly reporting the presence or absence of a target value change in a memory probe following the blank delay period. Previous studies have demonstrated: 1) lower response accuracy as the number of relevant items to be remembered increases, 2) lower response accuracy in filtering conditions relative to storage conditions when the number of relevant items is held constant across conditions, and 3) individuals with larger storage capacities show smaller costs in response accuracy in the filtering condition.

In the current proposal, we will be able to directly measure the effects of chemotherapy treatment on storage capacity mechanisms as they apply to the amount of information that can remembered and inhibitory control mechanisms as they apply to the suppression of irrelevant information.

Mobile cognitive testing. To track the timecourse of cognitive impairment between chemotherapy treatment cycles, patients will be given the option to complete customized attention tasks at home using BrainBaseline (Digital Artefacts), a mobile cognitive testing platform for use on a personal iPad or iPhone. De-identified data will be wirelessly transferred to HIPAA compliant servers maintained by Digital Artefacts.

Electrophysiology

The goal of Specific Aim 2 is to measure scalp electrophysiology to examine chemotherapy-related impairments in the neural mechanisms of attention on the timescale of milliseconds. To this end, we selected electrophysiological components that isolate four specific attention mechanisms: 1) *deployment speed* – time required to rapidly shift attention from one location to another, 2) *target enhancement* – amount of neural resources allocated towards selection of target item, 3) *distractor suppression* – amount of neural resources allocated towards inhibition of distractor item, and 4) *online storage* – amount of resources allocated toward storing target items in mind.

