Contralateral Delay Activity (CDA). The CDA component has been used in multiple empirical studies to examine neural mechanisms of attention specific to storage capacity because it tracks both which information is being stored in mind and how much information is being stored in mind ^{75,76,84}. The CDA component is a sustained relative negative amplitude modulation in posterior electrodes that onsets at approximately 300-400 milliseconds, with more negative amplitudes occurring in electrodes contralateral to the remembered visual field (Figure 4 right panel). CDA *amplitude* tracks online storage, where larger amplitudes suggest that more items are stored in mind^{75,76}. Here, the CDA will be used to measure chemotherapy-related differences in storage capacity during the filtering task.

Figure 4: Electrophysiological Components: N2pc (Left), Pd (Middle), CDA (Right)

Driving Simulation

The goal of Specific Aim 3 is to implement simulations of driving scenarios that integrate laboratory-based attention mechanisms into a naturalistic environment that requires the coordination of multiple cognitive domains, including attention. By selectively challenging distinct attention mechanisms under different driving conditions and loads (e.g. traffic, pedestrians, road signs), we will be able to evaluate how impairments in attention affects driving outcomes. Broadly speaking, the goal of testing patients in simulated driving scenarios is to determine how computer-based cognitive tasks (SA1) translate into real-world driving behavior.

Car following task. The car following task requires drivers to follow a lead vehicle at a constant distance of two car lengths^{85,86}. During this task, the lead vehicle pseudo-randomly changes its velocity, requiring drivers to vigilantly attend the lead vehicle to avoid an incursion while maintaining the instructed two-car length distance. Critically, the lead vehicle will occasionally brake during the drive, requiring drivers to rapidly brake in order to avoid collision. If attention is not fixed on the lead vehicle, an accident will likely occur. Outcome measures for the car following task include: 1) *mean distance* between lead vehicle and driver, 2) *brake delay*, measured as the delay between lead vehicle and driver braking time, and 3) *crash*, a binary variable that indicates if a collision occurred.

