While we realize we will not have sufficient power to declare smaller effects statistically significant, as this is a pilot study, it will allow us to estimate effect sizes for a number of outcomes to conduct fully powered studies. In future large-scale confirmatory studies, with a sample size of 32 per group, we will have 80% power to detect a standardized effect size of 0.65 (a medium to large effect) for within group changes, and an effect size of .9 for between group differences. These power calculations assume a two-tailed alpha of 0.01 to informally adjust for multiple comparisons and multiple testing. A standardized effect size of 0.65 corresponds to a 10% difference in response time from healthy controls (mean=1394.75, standard deviation = 213.23). This sample size will allow adequate power to detect medium to large effects within group, and large effects between groups.

Statistical Analysis. To assess the data collected, for each group, we will first produce frequency tables, calculate descriptive statistics, and create univariate graphs (e.g. box-plots, histograms) on the

predictor and response variables to investigate distributional properties and check for outliers in the data. Although the specific statistical models that we will use to test our formal hypotheses and to calculate confidence intervals will depend on the outcome distributions that we observe in our data, we anticipate using linear mixed models and generalized linear mixed models, as appropriate. This modeling approach allows us to properly account for the distribution of the outcome measure while also properly modeling repeated effects and adjusting for potentially confounding variables. Confidence intervals of all effects will be calculated in order to assess clinical significance of statistical results.

We will employ linear mixed models and general linear models to **assess** within-subject, betweensubject, and mixed effects of:

- Behavior:
 - Capture condition, stimulus ISI, and treatment group on response time measures in the Capture Task
 - Filtering condition, storage load, and treatment group on response accuracy measures in the Filtering Task
- Driving simulation:
 - Treatment group on response time measures in the Visual Search Task
 - Treatment group on lead car distance variability, brake time, and number of incursions during the Car Following Task
- □ Electrophysiology:

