 - Capture condition, stimulus ISI, and treatment group on Pd (amplitude, latency) and N2pc (amplitude, latency) measures during the Capture Task of the Attention Battery
 - Filtering condition, storage load, and treatment group on N2pc (amplitude, latency) and CDA (amplitude) measures during the Filtering Task of the Attention Battery
 - Treatment group on N2pc (amplitude, latency) and Pd (amplitude, latency) measures during the Visual Search Task of the Driving Simulation

Our primary hypothesis is that chemotherapy treatment negatively affects core neural mechanisms of attention. Here, we present predictions for how chemotherapy would affect outcome measures from each task and electrophysiological measure, where specific predictions are given based on how impairments in different attention mechanisms would affect the pattern of data observed in each task.

Attention Measures

Capture task. Two dissociable mechanisms of attention are measured in this task. First, *inhibitory control* is required to suppress the processing of the capture display; inhibitory control mechanisms will be tracked by the Pd component. Second, *disengagement speed* is required to rapidly release attention from capture displays to prepare for the subsequent search display; disengagement mechanisms will be tracked by the N2pc component. There are three possible predictions for impairments in each attention measured in the capture task.

- Hypothesis 1: Inhibition effect/No disengagement effect. Relative to comparison subjects, this hypothesis predicts a chemotherapy-related: 1) increase in response time differences between contingent and singleton capture conditions, 2) increase in Pd amplitude, and 3) decrease in N2pc amplitude.
- Hypothesis 2: No inhibition effect, disengagement effect. Relative to comparison subjects, this hypothesis predicts a chemotherapy-related: 1) increase in response times in both capture conditions, 2) decrease in N2pc amplitude, and 3) no difference in Pd amplitude.

Hypothesis 3: Inhibition effect, disengagement effect. Relative to comparison subjects, this hypothesis predicts a chemotherapy-related: 1) increase in response times in both capture conditions, 2) increase in response time differences between contingent and singleton capture conditions, 3) increase in Pd amplitude, and 4) decrease in N2pc amplitude.

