Filtering task. Two dissociable mechanisms of attention are measured in this task. First, *inhibitory control* is required to suppress the encoding of distractor items; inhibitory control mechanisms will be tracked by both the N2pc and CDA electrophysiological components. Second, sufficient *storage capacity* is required to maintain multiple items in working memory during the delay period; storage capacity will be tracked by the CDA electrophysiological component. There are three possible predictions for impairments in each attention mechanism measured in the filtering task.

- Hypothesis 1: Capacity effect, no inhibitory control effect. Relative to comparison subjects, this hypothesis predicts a chemotherapy-related: 1) decrease in response accuracy in both storage and filtering conditions, 2) decrease in CDA amplitude, and 3) no difference in N2pc amplitude.
- Hypothesis 2: No capacity effect, inhibitory control effect. Relative to comparison subjects, this hypothesis predicts a chemotherapy-related: 1) decrease in response accuracy only in the filter condition, 2) increase in N2pc amplitude, and 3) increase in CDA amplitude.
- Hypothesis 3: Capacity effect, inhibitory control effect. Relative to comparison subjects, this hypothesis predicts a chemotherapy-related: 1) increase in response accuracy differences between filtering and storage conditions, 2) increase in N2pc amplitude, and 3) increase in CDA amplitude.

Car following task. According to the hypothesis that chemotherapy treatment impairs *processing speed*, a chemotherapy-related decline should be observed in car-following performance because fewer resources would be available for processing lead vehicle events. Specifically, delayed processing would lead to delayed updating of lead vehicle driving information, which would lead to greater variability in car-driver distance and longer delay in driver brake onset, where longer brake delays would lead to more crashes.

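### The filtering-task patterns that label a storage-capacity effect make no use of storage load, so non-specific lapses of attention could be reported as lost capacity

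*Combined protocol and SAP*

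**What the plan says.** Section 5.0, Attention Battery, defines storage capacity as the "number of items that can be simultaneously attended". The filtering task is one of the tasks chosen to isolate it. The task is scored by accuracy alone: "Performance is measured as response accuracy of correctly reporting the presence or absence of a target value change in a memory probe". The same subsection expects "lower response accuracy as the number of relevant items to be remembered increases", so load is varied within the task.

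Section 10.0, Statistical Analysis, includes load in the models. For behaviour the listed effects are "Filtering condition, storage load, and treatment group on response accuracy measures in the Filtering Task". For EEG they are "Filtering condition, storage load, and treatment group on N2pc (amplitude, latency) and CDA (amplitude) measures during the Filtering Task".

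Section 10.0, Attention Measures, then says which pattern points to which mechanism. Filtering-task Hypothesis 1 (capacity effect without an inhibitory effect) predicts "decrease in response accuracy in both storage and filtering conditions, 2) decrease in CDA amplitude, and 3) no difference in N2pc amplitude". Hypothesis 3 (both effects) predicts a wider accuracy gap between filtering and storage conditions, with larger N2pc and CDA amplitudes. None of the three filtering hypotheses mentions load. On the CDA, Section 5.0 says that "larger amplitudes suggest that more items are stored in mind".

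**The concern.** A capacity limit is a statement about load. It should cost little while the display holds fewer items than a person can store, and it should show once the display exceeds that number. A fall in accuracy in both conditions does not test this. Off-task trials, fatigue or poor encoding would lower accuracy in both conditions with the number of storable items unchanged.

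Aim 1 sets out to separate attention into distinct mechanisms, and Section 5.0 itself expects anemia-related fatigue in the patients. The pilot is also meant to supply effect sizes for larger studies. A general loss of accuracy labelled as a capacity deficit would carry forward into the choice of outcome and the size of those studies.

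**Working it through.** The plan states no figure on this point, so there is none to reproduce. The check asks whether the stated criteria can tell lapses from lost capacity.

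**Inputs.** From the documents: capacity in items, accuracy as the outcome, load varied, 15 per group. Assumed, because the text does not give them: load levels 2, 4 and 6; capacity K = 3 items; a slots-plus-guessing model with chance at 50%; lapses on 10% of trials, answered at chance; no lapses in the reference case. The task figure is not available and may give the loads, so their absence from the text is not counted as a fault.

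**Accuracy.** With load N and lapse rate l,

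accuracy = 0.5 + 0.5 × (1 − l) × min(1, K/N).

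| | N = 2 | N = 4 | N = 6 | Mean |
|---|---|---|---|---|
| K = 3, no lapses | 100 | 87.5 | 75.0 | 87.5 |
| K = 3, 10% lapses | 95.0 | 83.75 | 72.5 | 83.75 |
| K = 2.5, no lapses | 100 | 81.25 | 70.8 | 84.0 |
| Loss from lapses | 5.0 | 3.75 | 2.5 | 3.75 |
| Loss from lower capacity | 0 | 6.25 | 4.2 | 3.5 |

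The loss from lapses is 0.5 × l × min(1, K/N). This is positive at every load and at any effective capacity, so it appears in the filtering condition as well as the storage condition. The mean over loads hardly separates the two explanations. The contrast of the two higher loads with the lowest does:

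- lapses: (3.75 + 2.5)/2 − 5.0 = −1.9 points;
- lower capacity: (6.25 + 4.2)/2 − 0 = +5.2 points.

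**Range.** Other load sets between 1 and 6 items, capacities of 2.5 or 3.0 and lapse rates of 10% or 20% were tried. Lapses then gave the same mean accuracy as a capacity fall from 3.0 to between 1.75 and 2.46 items, or from 2.5 to between 1.40 and 2.01. At the lowest load, lapses cost 5 to 10 points. The matched capacity loss cost 0 there when the lowest load was 1 item, and 0 to 6.7 points when it was 2.

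**CDA.** Assume amplitude proportional to the items stored, min(K, N), and no CDA on lapse trials. Ten percent lapses lower the averaged CDA by 10% at every load. A capacity fall from 3 to 2.5 changes items stored from 2, 3, 3 to 2, 2.5, 2.5. Averaged over loads that is 1 − 7/8 = 12.5%, made up of 0%, 16.7% and 16.7% by load. The load-averaged CDA therefore moves in the same direction and by a similar amount under either explanation.

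**N2pc.** The unchanged-N2pc criterion has no margin. Assume a between-person coefficient of variation of 50%, so that a 10% fall is 0.10/0.50 = 0.2 SD. A two-sample t-test with 15 per group at two-sided 5% has 8.3% power (noncentral t), so such a fall would go undetected about 92% of the time. At two-sided 1%, the level the plan states for its future study, 80% power needs a difference of 1.33 SD.

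**All three parts together.** The same power argument applies to the CDA criterion. With the same assumed variation, a 10% CDA fall is also 0.2 SD and is found about 8% of the time. The full pattern cannot occur more often than its least likely part, so 10% lapses would satisfy it in at most about 8% of studies. At 20% lapses the CDA fall is 0.4 SD, power is about 18%, and the bound rises to about 18%.

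**The case against.** The strongest reply has four parts.

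- *Load is already in the plan.* It is a named factor in the accuracy and EEG models, and a group-by-load contrast can be drawn from them. A reader might infer that the analysis ignores load; the documents contradict that. What remains is that the model list names no interaction, and the text that attaches mechanism labels does not say which load pattern means lost capacity.
- *Accuracy is not the only criterion.* Hypothesis 1 also requires a lower CDA and an unchanged N2pc. A reader might infer that lapses would be reported as capacity loss. The bound above does not support that: modest lapses would seldom meet all three parts at 15 per group. That protection comes from low power, which would hide a true capacity loss as well, and not from any ability to tell the two apart. It weakens with more lapses, less variable CDA or larger groups.
- *These are predictions in a pilot, not a decision algorithm.* This is fair, and it limits the severity. They are still the only place where the plan links filtering-task results to mechanisms.
- *Fatigue and mood are measured.* Blood counts, depression and medication are candidate covariates, kept if linked to performance. This helps in part, but none of them measures off-task trials.

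The inputs to the illustration are assumed. Simulated detection rates for the accuracy criterion vary widely with design details that the plan does not state, so none is relied on here.

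**Conclusion.** The point stands in a limited form. Capacity is defined in items, the outcome is raw accuracy, no item-based score is given, and neither Hypothesis 1 nor Hypothesis 3 uses load. Non-specific lapses meet the accuracy part of Hypothesis 1 with capacity intact, and the two EEG criteria as worded do not cleanly exclude them. Lapses could therefore be reported as lost capacity; the documents do not show that they would be. The mimicry applies to Hypothesis 1. Under the model above, lapses shrink the filtering-storage gap that Hypothesis 3 expects to widen. The fault in Hypothesis 3 is that its accuracy criterion says nothing about the number of items.

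The size is illustrative: mean losses of 3.75 and 3.5 points that overall accuracy can hardly tell apart, against load contrasts of −1.9 and +5.2 points that differ in sign. This rests on the slot model and on the assumed loads, capacity and lapse rate. The contrast separates best when the lowest load is well below capacity.

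**What to change.** In Section 10.0, Attention Measures, Filtering task:

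- Restate the behavioural criterion for a capacity effect in Hypotheses 1 and 3 as a group-by-visit-by-load contrast from the planned model, with accuracy falling more at the higher storage loads than at the lowest.
- State that an equal or larger fall at the lowest load will be reported as a general accuracy effect and not as capacity loss.
- Optionally, add an item-based score from storage trials, K = load × (hit rate − false-alarm rate) at loads above capacity, with a lapse term estimated from the lowest load. This is one scoring convention; modelling accuracy by load is enough.

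The change needs wording and, if the score is used, a derived variable from responses already recorded. It needs no new testing. The cost is precision: the load interaction is estimated less precisely than the overall mean, so with 15 per group it should be reported as an estimate with a confidence interval.

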ignored other prevalent tumor types; 2) few studies have examined dose-response effects of specific chemotherapy treatments on cognitive impairment; 3) neuropsychological tests used to characterize chemotherapy-related cognitive impairment provide limited resolution for understanding impairments of specific neural mechanisms; 4) neural factors associated with cognitive impairment have not been sufficiently distinguished from non-neural (e.g. psychosocial) factors. Despite these limitations of current research, chemotherapy-related cognitive impairment affects everyday function and quality of life in cancer survivors. This is a problem that merits further investigation and cannot be ignored.

To overcome these critical limitations of current research on chemotherapy-related cognitive impairment, we propose a two-year pilot study that aims to systematically examine the influence of cancer stage and treatment toxicity on attention abilities in patients diagnosed with a hematological malignancy (HM). We will establish and measure a core battery of behavioral and electrophysiological measures of attention to assess the impact of chemotherapy on this central cognitive ability.

Our specific aims are to:

SA1. Quantify chemotherapy-related attention impairments in HM patients

- H1a. HM groups will not differ from comparison subjects in attention abilities prior to chemotherapy and will perform worse than comparison subjects without cancer or chemotherapy after treatment.
- H1b. Degree of chemotherapy exposure will predict magnitude of attention impairments.
- SA2. Quantify the link between chemotherapy-related attention impairments and electrophysiological measures of attention in HM patients and comparison subjects
 - H2a. HM groups will not differ from comparison subjects in electrophysiological measures of attention prior to treatment but will differ from comparison subjects without cancer or chemotherapy after treatment.
 - H2b. Degree of chemotherapy exposure will predict magnitude of changes in electrophysiological measures of attention.
 - H2c. Electrophysiological measures of attention decline will be predicted by concurrent impairments in behavioral measures of attention (as in H1b).
- SA3. Quantify the effects of chemotherapy-related attention impairment on complex real-world behavior measured in controlled-simulations of on-road driving scenarios designed to challenge driver attention abilities

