□ Response time (Capture Task) and response accuracy (Filtering Task) Electrophysiology

□ Amplitude and latency of N2pc, Pd, and CDA electrophysiological components Driving Simulation

- Response time (Visual Search Task)
- Brake time, mean following distance, and number of incursions (Car Following Task)
 CRP
 - Concentration levels of circulating inflammatory proteins

OCT

Surface area and volume of retinal ganglion cell layer and optic nerve fiber

Given that we are not proposing an intervention trial our primary outcome measures will not be related to the progression of HM.

Section 7.0 Study Parameters:

Summary of Study Events and Durations. Each study visit is anticipated to take approximately 2.5 hours to complete. Table 1 contains a summary for the schedule of study events to occur at each research component. Study induction takes place at the beginning of Visit 1. Time requirements for research participants at each study event are as follows:

- □ Study Induction (~.5 total hours):
 - Informed consent (20 minutes)
 - Demographic Information (10 minutes)
 - Comorbidity Index (conducted offline)
 - Anemia Evaluation (conducted offline
- □ Each Study Visit (~2.5 total hours):
 - Cognitive Battery (40 minutes)
 - Electrophysiology (15 minutes)
 - Driving Simulation (20 minutes)
 - Neuropsychological Exams (45 minutes)
 - Health & Mobility Questionnaires (10 minutes)
 - OCT (10 minutes)
 - Blood Collection (10 minutes)

	Pre- Induction	Study Induction	Visit 1 (Month 0)	Visit 2 (After Month 1 or 1 treatment	Visit 3 (After Month 3 or 3 treatment
				cycle)	cycles)
HM Diagnosis	X				
Control Group ID	X				
Informed Consent		Х			
Demographic Information		Х			
Comorbidity Index		Х			
Anemia Evaluation		Х			
Chemotherapy Treatment			X	X	X
Cognitive Battery			X	Х	Х
Electrophysiology			X	Х	X
Driving Simulation			X	Х	Х
Neuropsychological Exams			X	X	X
Health & Mobility Questionnaires			X	X	X

OCT		Х	Х	X
Blood Collection/ Protein Assay		Х	X	X

Section 8.0 Drug Formulation and Procurement:

This pilot study is not a pharmaceutical trial.

Section 9.0 Toxicity and Adverse Event Reporting Guidelines:

This research has been classified as Minimal Risk.

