There is the potential to detect cognitive impairment in research participants during cognitive assessment. After consent, if a participant receives an MMSE score of 20 or less, they will be discontinued from the study. If cognitive impairment is identified, research personnel will proceed in the following way. First, the participant will be informed that an unexpected finding was encountered that may have clinical significance, and that the clinical significance is best determined in conjunction with his or her primary care physician. Next, research personnel will ask the participant for their permission to contact their primary care physician to help facilitate follow-up to determine clinical significance. The primary care physician will then be contacted and provided clinical context and concerns sufficient to allow for subsequent evaluation, workup, and treatment of any unexpected finding. If the participant refuses to have the research personnel directly contact their physician, the research personnel will offer the participant a written explanation that an abnormal neurological finding was encountered and the written material will include encouragement to have an evaluation, as well as a phone number of the Mind and Brain Health Labs to contact with questions or in case they change their mind.

Section 10.0 Statistical Considerations:

Our primary goal is to examine the effects of chemotherapy on behavioral and electrophysiological measures of cognitive ability in an understudied cancer population. To this end, analyses for the proposed pilot project will be performed on three groups: healthy controls (no cancer, no chemotherapy), very-low to intermediate risk HM patients receiving supportive care treatment (no chemotherapy), and intermediate to very-high risk HM patients receiving chemotherapy treatment.

Statistical Power. Although many of the statistical analyses will involve complex modeling procedures, the main emphasis of our aims and hypotheses is to determine differences between groups and pre-post treatment. Hence, the issue of statistical power can be addressed via consideration of the magnitude of standardized effect sizes that can be detected with reasonable probability. The current study aims to collect pilot data and demonstrate protocol feasibility for future studies and funding opportunities. As such, we plan to obtain 15 samples per group for a total sample size of 45.

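### Does the power paragraph present the within-group effect size of 0.65 as a difference from healthy controls?

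*Combined protocol and SAP*

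**What the plan says.** All of this is in Section 10.0 of the combined protocol and SAP. The Statistical Power paragraph sets the pilot at 15 per group, 45 in total, and gives the reason: "The current study aims to collect pilot data and demonstrate protocol feasibility for future studies and funding opportunities". It concedes that smaller effects will not reach significance and says the pilot will estimate effect sizes for later work.

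For future confirmatory studies with 32 per group, it then says "we will have 80% power to detect a standardized effect size of 0.65 (a medium to large effect) for within group changes". The same sentence continues with the other contrast: "for within group changes, and an effect size of .9 for between group differences". Alpha is two-tailed 0.01.

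The conversion to outcome units comes next: "A standardized effect size of 0.65 corresponds to a 10% difference in response time from healthy controls (mean=1394.75, standard deviation = 213.23". The paragraph closes with: "This sample size will allow adequate power to detect medium to large effects within group, and large effects between groups".

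The documents do not say whether 213.23 is the SD of a single visit or of a change between visits. They give no visit-to-visit correlation, and the sentence does not name the task. Response time is an outcome in two tasks: Section 6.0 lists "Response time (Capture Task) and response accuracy (Filtering Task", and the Statistical Analysis part of Section 10.0 includes "Treatment group on response time measures in the Visual Search Task".

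**The concern.** Section 10.0 attaches 0.65 to change within a group. The illustrating sentence takes that same 0.65 and describes it as a distance from healthy controls. In this study patients against controls is a between-group contrast; hypothesis H1a in Section 1.0 says that patients "will perform worse than comparison subjects without cancer or chemotherapy after treatment". The between-group effect size, 0.9, has no equivalent in outcome units.

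A reader planning the next study could therefore conclude that 32 per group is sized for a 10% difference between patients and controls. On the plan's own between-group figure the difference is nearer 14%, and an unadjusted comparison would have about an even chance of detecting 10%. Since the pilot is meant to support later studies and funding, a misreading here could be carried into a later sample-size argument.

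**Working it through.** **Inputs** (all from Section 10.0, Statistical Power): 32 per group; two-sided alpha 0.01; 80% power; effect sizes 0.65 (within) and 0.9 (between); mean 1394.75; SD 213.23.

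**1. The plan's power figures** (noncentral t)
- Within group, paired t-test, n = 32, d = 0.65: power 81.7%. The smallest effect with 80% power is 0.639.
- Between groups, two-sample t-test, 32 per group, d = 0.9: power 82.3%. The smallest effect with 80% power is 0.878.

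Both stated effect sizes reproduce, each with its own test.

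**2. The plan's conversion** (d × SD / mean)
- 0.65 × 213.23 = 138.6, and 138.6 / 1394.75 = 9.9%. The stated 10% reproduces.
- Conversely, 10% of 1394.75 is 139.5, and 139.5 / 213.23 = 0.654 SD.

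**3. The sentence read as a between-group contrast** (assumes 213.23 is a single-visit, between-subject SD)
- 0.9 × 213.23 = 191.9, and 191.9 / 1394.75 = 13.8%. The gap from 138.6 is 53.3 units.
- An unadjusted two-sample test of 0.654 SD with 32 per group at alpha 0.01 has 48.8% power; 80% would need 57 per group.
- Section 10.0 anticipates mixed models with repeated measures and covariates. With baseline adjustment at an assumed visit-to-visit correlation r and equal SDs, the effective size is 0.654 / √(1 − r²):

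| Assumed r | Power for a 10% difference |
|---|---|
| 0 (unadjusted) | 49% |
| 0.3 | 54% |
| 0.5 | 64% |
| 0.67 | 80% |
| 0.7 | 84% |

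**4. The sentence read as a within-group change**, with the control mean and SD only as reference values
- If 213.23 is already the SD of change, 0.65 is 9.9% and the sentence is right as it stands.
- If 213.23 is a single-visit SD, equal at both visits, and 0.65 is in units of the SD of change, the percentage is 0.65 × 213.23 × √(2(1 − r)) / 1394.75. That is 11.8% at r = 0.3, 9.9% at r = 0.5 and 7.7% at r = 0.7.

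**5. What depends on the sentence.** It states no power, sample size or test. The pilot's 15 per group is justified by feasibility and pilot data, not by 0.65, 0.9 or 10%. The models, outcomes and confidence intervals described under Statistical Analysis use none of these figures.

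**The case for a change.** The strongest case for an edit is that neither reading makes the sentence complete. Read literally, a distance from controls is a between-group contrast, and 0.65 is the wrong effect size for it. Read as a within-group change, 0.65 should be scaled by the SD of change, which the documents do not identify. Either way the reader cannot tell which contrast, which SD or which task is meant, and this is the only place where the power statement is put into outcome units. The repair would cost a sentence or two.

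Much of this stands. The phrase is ambiguous, the literal reading is the more natural one, and the missing detail is real. Two points weaken the case. The effect sizes are assigned to their contrasts shortly before the sentence and again directly after it, so the whole paragraph does not support the claim that 32 per group is sized for 10% between groups. And replacing 10% with 14% would not settle the matter: 14% assumes that 213.23 is a single-visit SD, which is exactly what the text leaves open. The 49% likewise describes an unadjusted comparison, and moderate baseline adjustment raises it considerably.

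**Conclusion.** The concern describes the wording accurately but does not call for a change. The only raw-scale illustration pairs the within-group effect size with wording that can be taken as a patient-control contrast. This is a clerical ambiguity: the conversion is correct (9.9%, stated as 10%), both power figures reproduce (81.7% and 82.3%), and no stated figure is wrong.

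If the sentence is misread, the gap is 10% against about 14%. The corresponding power for a 10% difference is about 49% unadjusted, or 54% to 84% with baseline adjustment at correlations of 0.3 to 0.7. These figures assume that 213.23 is a single-visit SD, and the adjusted range also assumes correlations that the documents do not give.

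The misreading would touch only a hypothetical study of 32 per group. That study would need its own calculation, and the pilot is designed to supply the effect sizes for it. Editing the sentence would leave the pilot's sample size, visits, analyses and interpretation exactly as they are.
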